Electronic-based personalised dental education for caries prevention in a disadvantaged population: a randomised controlled study

Protocol Number OHSRC00114

Oral Health Services Research Centre University College Cork, Ireland

Table of contents

Summary	3
Introduction	4
Location of study	6
Aim of study	6
Specific objectives	6
Investigator and research personnel	7
Ethics approval	7
Preparatory work	7
Study methodology	8
Sample size calculation	9
Subject recruitment	10
Training module for dental professionals	10
Baseline examination	10
Informed consent	10
Past caries experience	10
Plaque amount	11
Fluoride use	11
Related systemic diseases	11
Saliva tests	11
Dietary record/Questionnaire	12
Randomisation	12
Intervention	12
Follow-up examination	13
Data analysis	13
Infection control	14
Potential risks and benefits to participants	14
Data Management	
Timetable	
List of Protocol Appendices	
References	
Web links	17

Electronic-based personalised dental education for caries prevention in a disadvantaged population: a randomised controlled study

Summary

Although many studies have shown lower socioeconomic groups have a greater burden of dental disease than higher socioeconomic groups, studies have not shown the particular individual variability of caries risk within the lower socioeconomic groups. If individual variability exists, then personalised caries prevention and management are imperative. This project aims to investigate the effectiveness of an electronic-based assessment (Cariogram) and a personalised approach to caries prevention adopting personalised marketing techniques. An electronic marketing system modelled on Rapport Builder® will be developed to deliver electronic personalised educational messages for caries prevention each week to the subjects, based on their risk profile derived from the Cariogram.

To investigate the effectiveness of the approach, we will conduct an evaluator-blind randomised controlled study. Approximately 200 medical-card (proxy for low socioeconomic status) patients recruited from approximately 10 dental surgeries in Ireland will be randomly assigned to test and control groups. The caries risk profile of all subjects will be assessed using Cariogram at baseline and at six months. Once weekly for 24 weeks, the Test group will receive personalised educational text messages on caries prevention while the Control group receives non-personalised educational text messages. The average change in "chance to avoid new cavities" as measured by Cariogram before and after the intervention between the test and control groups will be compared using a two-sample two-sided t-test.

If the electronic personalised education system (EPES) for caries prevention proves successful, it represents a ground-breaking approach to reducing caries risk and building patient engagement in those with greatest need, adopting modern technologies to promote regular check-ups and better dental health. Furthermore, the concept could be adapted and applied to other lifestyle related diseases with individual variability.

Introduction

Although many studies have shown lower socioeconomic groups have a greater burden of dental disease than higher socioeconomic groups (Petersen, Bourgeois, Ogawa, Estupinan-Day, & Ndiaye, 2005), studies have not shown the particular individual variability of caries (tooth decay) risk within the lower socioeconomic groups. Caries risk may vary from person to person and may change during a person's lifetime; if individual variability exists, then personalised caries prevention and management are imperative. The literature suggests that providing caries prevention advice without reference to the individual's specific risk factors is not effective in achieving long-term behaviour change (Kay & Locker, 1998; Yevlahova & Satur, 2009).

Funding for this project has been provided through the 2014 *IADR/Unilever Social Entrepreneur Approach to Change Oral Health Behaviour Research Award*, administered by the International Association for Dental Research (IADR) and sponsored by Unilever (http://www.iadr.org/).

Location of study

The study will be administered from the Oral Health Services Research Centre in Cork University Dental School & Hospital. Patients will be seen by their General Dental Practitioners (GDPs) in the GDP surgeries. Text messages will be sent from the UK-based Text Magic service (https://www.textmagic.com/).

Aim of study

This project aims to investigate the effectiveness of an electronic-based caries risk assessment (Cariogram) with a personalised educational approach adopting personalised marketing for caries prevention in lower socioeconomic groups.

Specific objectives

The specific objectives are:

- 1. To assess the influence on seven caries risk factors:
 - frequency of fermentable-carbohydrate intake (sugars)
 - amount of plaque present
 - bacterial counts

 - ♦ lactobacilli (LB)
 - use of fluorides
 - salivary flow
 - salivary buffering capacity
- 2. To assess whether there is an increase in patient engagement with the dentist
- 3. To assess the prevalence and distribution of the risk factors indicated along with past caries experience and systemic diseases and conditions such as cardiovascular

- disease, diabetes and obesity
- To assess the knowledge, behaviour and patient satisfaction relating to 4. personalised caries prevention.

Investigator and research personnel

Role	Name	Address	
Principal	[name]	Restorative Dentistry, University	
Investigator		Dental School & Hospital, University	
		College Cork	
Co-investigator	[name] BDS,	Oral Health Services Research Centre,	
	MFGDP(UK), MDPH	University Dental School, Cork	
	Senior Dental Surgeon	HSE South Cork ISA	
Co-investigator	[name]	Oral Health Services Research Centre,	
	BEd(Japan),	University Dental School, Cork	
	DDS(Japan), MDPH		
Laboratory	[name]	Oral Health Services Research Centre,	
Technician		University Dental School, Cork	
Statistician	To be recruited		
Programmer	[name]	School of Computer Science and	
	Undergraduate student,	Information Technology, University	
	supervised by [name] Cork	
	[name]		

Ethics approval

This project has had the approval of the Clinical Research Ethics Committee of the Cork Teaching Hospitals.

Preparatory work

[name] has been conducting a questionnaire survey on personalised caries prevention

in a Japanese population as her PhD project. That questionnaire has been adapted for use in this project. A Japanese non-profit organization (NPO), of which [name] is the President, has adapted Rapport Builder® for sending oral health messages to its members. This project will work on the adapted version of Rapport Builder® (Figure 2).

Figure 2. Example of a text message to be used in this study. Simple messages are delivered weekly in a humorous manner to engage the attention of the target audience.

Hi! Prevent tooth decay by making smart & healthy food choices: foods & drinks high in sugar can lead 2 tooth decay & weight gain. Eat smart, stay healthy!

Study methodology

This project is a randomised controlled study. The null hypothesis is that no difference exists between the group receiving EPES and the group receiving non-personalised information.

The innovativeness of this project made it difficult to set the intervention interval. We considered an interval of more than six months, however we wished to maintain subject engagement and to assess the study outcomes and innovativeness. In addition, the Cariogram manual suggests re-assessment in six months for high-risk patients.

Train dental professionals

Baseline exam

Culture of bacteria Randomisation

Test group
Personalised txt messages weekly

Control group
Non-personalised txt messages weekly

Follow-up exam

The project process is set out below (Figure 3).

Figure 3. Process chart. Orange boxes indicate activities carried out at the Oral Health Services Research Centre (OHSRC); green boxes indicate activities at dental surgeries.

Culture of bacteria
Data analysis

Sample size calculation

To estimate the sample size, we conducted a power calculation based on previous Cariogram studies. Where the average baseline Cariogram "chance to avoid new cavities" score is 36, with a mean between-subject standard deviation of 21.6, a sample of 64 subjects per group is required. This will provide an 80% power with a margin of error of 0.05, to detect a "chance to avoid new cavities" of at least 30% relative to the control group over the 6-month duration of the study.

To ensure adequate numbers in each group at six months to permit appropriate analysis, and minimising the risk of type II error, 100 subjects will be entered in each group at baseline.

Subject recruitment

An estimated 200 medical-card (i.e. proxy for low socioeconomic status) patients will be recruited from approximately ten general dental surgeries in Ireland. The inclusion criteria are (i) 19–70 years of age, (ii) medical-card holder, (iii) \geq 20 teeth present, (iv) not pregnant, (v) ability to use text messaging and (vi) willingness to participate in the project.

Training module for dental professionals

[name] and [name] explained the project protocol to the participating dental professionals, and will train them in the study procedures. [name] has worked extensively with the Cariogram. The dental professionals are being calibrated for DMFT/DMFS and plaque index. This training is being carried out in the OHSRC.

Baseline examination

At the first appointment in the general dental surgery, the study will be explained and informed consent will be obtained prior to examination. The dental practitioner will interview the patient (fluoride use, related systemic diseases / conditions), collect saliva samples (determine salivary flow rate, salivary buffer capacity, bacteriological tests, CRT® Ivoclar Vivadent, Liechtenstein), examine (past caries experience, plaque amount) and provide a questionnaire and a dietary record form for the subject. The CRT® agar culture, history form including fluoride use and systemic diseases and oral examination form will be sent to the OHSRC within a day from the dental surgery by car.

Informed consent

If the patient meets the inclusion criteria listed above, they will be invited by the general dental surgeon to read the information sheet for patients. If they agree to participate in the project, they must sign the informed consent form.

Past caries experience

Past caries experience will be recorded for each tooth surface. Recording codes are outlined in Appendix 5 of this protocol.

Plaque amount

The Plaque Index (PI), according to Silness and Löe (1964) will be used. Recording codes are outlined in Appendix 5 of this protocol.

Fluoride use

Relevant information on fluoride use will be obtained through patient interviews. The patient will be asked:

- if the patient uses fluoridated water,
- if the patient uses fluoridated tooth paste,
- if the patient uses additional fluoride measures such as rinses and varnishes frequently,
- if the patient uses additional measures such as rinsing and varnishes, infrequently.

Related systemic diseases

The relevant information on systemic diseases will be obtained by patient interviews only. The patient will be asked whether he/she suffers from diseases / conditions such as:

- autoimmune diseases, like Sjögren's syndrome
- diabetes mellitus
- anorexia nervosa
- visually impaired
- any manual dexterity which might cause them difficulties with cleaning their teeth properly.
- any disease, which requires continuous medication that, for example, affects their saliva secretion. Details of any concomitant medications will be recorded.
- any condition requiring radiation to the head-neck region

Saliva tests

The general dental surgeon will collect saliva samples in a standardised format,

from participating patients to determine salivary flow rate, saliva buffering capacity and bacteriological testing. Details of saliva sampling procedures are outlined in Appendix 3 of this protocol.

The laboratory technician in the OHSRC will incubate and read the CRT® slides in accordance with the manufacturer's instructions.

Dietary record/Questionnaire

The patient will be provided with the 3-day dietary record and the study questionnaire, along with a stamped, addressed envelope for return of completed documents to the OHSRC.

Randomisation

The subjects will be stratified for "chance to avoid new cavities" by quartiles (0–20%, 21–40%, 41–60%, 61%–100%) and randomly allocated to Test or Control group by the statistician.

Intervention

A report of their caries risk assessment, along with their output chart as generated by Cariogram, will be sent by post to the subjects in the Test group. The subjects in the Control group will be sent only general information (not generated by Cariogram) on caries prevention, also by post. A €20 voucher will be sent to all subjects as a token of appreciation for participating in the study.

Once weekly for 24 weeks, the Test group will receive personalised oral health text messages on caries prevention while the Control group receives non-personalised text messages offering general oral healthcare advice.

Table 1 shows how to calculate numbers of text messages allocated to each risk sector for the Test group. All subjects in the Control group will receive the same six non-personalised text messages for each risk sector. All oral health messages are evidence-based (Levine and Stillman-Lowe 2009).

Table 1. How to calculate numbers of text messages of each sector. Using the example in Figure 1, over the 24 week study period, the EPES will send this patient nine text messages on bacteria (33/84), three text messages on diet (11/84), two text messages on circumstances (7/84) and nine text messages on susceptibility (33/84).

Sector (Risk Factor / Risk Indicator)	Percentage contribution calculated with the Cariogram chart (%)	Proportion contribution of each sector to the overall calculated risk (%)	Number of texts on each sector to be sent text messages
Bacteria (plaque and mutans streptococci)	33	39	9
Diet (content and frequency)	11	13	3
Circumstances (previous caries experience, co-exiating diseases)	7	8	2
Susceptibility (available fluorides, saliva properties)	33	39	9
Total of the four sectors	84	100	24
"Chance to avoid new cavities"	16		
Total of the five sectors	100		

Follow-up examination

At the second appointment, six months after the baseline examination, the same data collection procedures as at baseline (except the taking of informed consent) will be followed. After the six-month assessment, both Test and Control group subjects will be sent their baseline and follow-up output charts and their personalised caries prevention advice as generated by Cariogram, along with their reward for completing the study (€30 voucher), by post from the OHSRC.

Data analysis

[name] will enter baseline and six-month follow-up data into the Cariogram software programme and generate Cariogram reports for each patient at each timepoint.

The data will be analysed using a statistical package (SPSS/SAS) by [name] with the aid of a statistician. The average of "chance to avoid new cavities" as measured by Cariogram as well as the seven risk factors before and after the intervention between the test and control groups will be compared using a two-sample two-sided t-test. In addition, the measured risk factors/indicators and questionnaires results will be analysed for the third and fourth research objectives.

Infection control

Infection control in accordance with the Dental Council Ireland guidelines, (http://www.dentalcouncil.ie/g_crossinfection.php) and Cork University Dental School and Hospital will be adhered to.

Potential risks and benefits to participants

The dental examination carries no risk to the subjects and will only be undertaken with their consent and the co-operation. Standard infection control measures will be observed, as mentioned above. As there is currently no such comprehensive caries risk assessment for medical card patients in Ireland, the dental examination offers the benefit of notifying the subjects how to prevent dental caries more effectively than traditional prevention. CRT® tests are for free. At six months, the subject gets two reports of their caries risk assessments (baseline and follow-up). There will also be a total of €50 (vouchers for €20 at baseline and €30 at 6-months follow-up) reward for each patient participating in the study.

The dental practitioners will benefit by learning about caries risk assessment with Cariogram. Patients' participation in the project should make their caries management more effective in the dental surgeries and improve their motivation to visit for regular check-ups. The dental practitioners will be given full acknowledgement for their work in any publications or reports generated from the project.

If this EPES for caries prevention proves successful, it represents a ground-breaking approach to reducing caries risk and building patient engagement in those with greatest need, adopting modern technologies to promote regular check-ups and better dental health. Furthermore, the concept could be adapted and applied to other lifestyle related diseases with individual variability, such diseases are not only expensive to manage for the patient but also to treat, placing a significant burden on society.

Data Management

All personal and clinical data will be treated as confidential. Data from the clinical examination will be entered onto the paper Case Report Form, the original of which will be sent to the OHSRC. Data will be entered into an Excel spread sheet. Subject records will be retained in compliance with the requirements set out under the Dental Council. All files with patients' personalised data (full name, gender, age, address, and mobile number) will be password protected. Computers will be encrypted. The server of Rapport Builder® is protected from malware.

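### The 64 per group and 80% power are correct for a single-time-point score, but the Summary tests change from baseline, to which the 80% carries over only if the baseline to six-month correlation is about 0.5

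*Protocol*

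**What the plan says.** The Sample size calculation section takes its inputs from previous Cariogram studies. It puts the average baseline score at 36 and states that, "with a mean between-subject standard deviation of 21.6, a sample of 64 subjects per group is required". It continues, "This will provide an 80% power with a margin of error of 0.05", the target being "to detect a 'chance to avoid new cavities' of at least 30% relative to the control group". To protect numbers at six months, 100 per group will be entered. No expected loss rate is given.

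The comparison is described twice. The Summary has "The average change in 'chance to avoid new cavities' as measured by Cariogram before and after the intervention between the test and control groups", which "will be compared using a two-sample two-sided t-test". The Data analysis section names the same test, applied to the average score and the seven risk factors before and after the intervention, and does not use the word change.

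The protocol states no SD of change, no correlation between the two visits and no target difference in points.

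**The concern.** The SD of 21.6 describes how far people differ from one another on one occasion. The Summary's outcome is the difference between two scores from the same person. Its spread depends on how strongly those scores are correlated, which the protocol does not say. A power figure computed with the first SD is therefore not automatically the power of a test on the second quantity.

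At stake is whether the stated 80%, and the implied allowance for loss between 100 and 64 per group, can be relied on for the test that the Summary names. This is not a detail left for a later analysis plan, because the protocol itself fixes the SD, the sample size, the power and the test.

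Two phrases make the paragraph harder to check. The effect is worded as a level of the score, without a word such as increase or difference, for an outcome that is itself a percentage. The significance level is called a margin of error.

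**Working it through.** **Inputs.** From the Sample size calculation: baseline mean 36, between-subject SD 21.6, effect 30%, 0.05, power 80%, 64 per group required, 100 per group entered. From the Summary and Data analysis: two-sided two-sample t-test. Assumed, because the protocol does not give them: the correlation r, and an SD of 21.6 at six months as well as at baseline.

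**Step 1: reproduce the plan's figure.**
- Difference: 0.30 × 36 = 10.8 points.
- Standardised difference: 10.8 / 21.6 = 0.5.
- Exact two-sample t calculation, two-sided 0.05, power 80%: n = 63.8, so 64 per group. Power at 64 is 80.1%.
- If all 100 per group are analysed, power is 94%.

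The printed figure reproduces. Other readings of the paragraph do not give it:

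| Reading | n per group |
|---|---|
| 10.8 points, two-sided 0.05 | 64 |
| 10.8 points, one-sided 0.05 | 50 to 51 |
| 30 points, two-sided 0.05 | 9 to 10 |
| score of 30 against 36 (6 points), two-sided 0.05 | about 204 |

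**Step 2: the same difference tested on change.** With equal SDs at both visits,

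SD of change = 21.6 × √(2(1 − r)).

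For example, at r = 0.3 this is 21.6 × √1.4 = 25.6, and the standardised difference is 10.8 / 25.6 = 0.42.

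| r (assumed) | SD of change | n per group for 80% | Power at 64 | Power at 100 |
|---|---|---|---|---|
| 0.2 | 27.3 | 102 | 60% | 79% |
| 0.3 | 25.6 | 89 | 66% | 84% |
| 0.4 | 23.7 | 77 | 73% | 90% |
| 0.5 | 21.6 | 64 | 80% | 94% |
| 0.6 | 19.3 | 52 | 88% | 98% |
| 0.7 | 16.7 | 39 | 95% | over 99% |

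Power at 64 is below 80% when r is under 0.5 and above 80% when r is over 0.5. With all 100 per group analysed, it falls below 80% only when r is about 0.2 or less.

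**Step 3: tolerable loss if change is tested.** At r = 0.5, 64 evaluable per group are needed, so 100 allows a loss of 36%. At r = 0.3, 89 are needed, so 100 allows 11%.

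**Step 4: six-month score adjusted for baseline.** The residual SD is 21.6 × √(1 − r²), which never exceeds 21.6.

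| r (assumed) | Residual SD | Power at 64 |
|---|---|---|
| 0 | 21.6 | 80% |
| 0.3 | 20.6 | 84% |
| 0.5 | 18.7 | 90% |
| 0.7 | 15.4 | 98% |

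Under this analysis 80% is a floor at 64 per group, provided the SD at six months is also 21.6. The model spends one degree of freedom on the baseline score, which leaves the rounded figures unchanged.

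**The case against.** The strongest reply is that the Data analysis section, where the test is specified, compares averages and never says change. Read as a comparison of average six-month scores, it is exactly the test that was powered. This stands in part: the calculation fits one of the two descriptions. It does not settle the matter, because that section also speaks of before and after the intervention, and the Summary plainly says change. The two sections still have to be brought into line.

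A reader might infer that the trial is underpowered. The documents do not support that. No correlation is given, so the direction is unknown. Some inputs to the score, such as previous caries experience and co-existing diseases, are unlikely to reverse in six months, which argues against a correlation near zero. Entering 100 per group adds a further cushion, although it shrinks with loss to follow-up.

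A reader might also infer an arithmetic error, or that the detectable effect cannot be known. Neither holds. The number 64 reproduces, and of the readings tried only 10.8 points at two-sided 0.05 yields it. The wording of the 30% effect and of the margin of error changes no number; both are matters of clarity.

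Last, adjusting for baseline is not in the protocol, so recommending it changes the stated t-test. That is correct, and the fix counts it as a cost.

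**Conclusion.** The point holds in a limited form. The 64 per group and 80% power are right for a 10.8-point difference in a single-time-point score with SD 21.6. They are not shown to be right for the change-score test in the Summary, where power at 64 runs from about 60% at r = 0.2 to 95% at r = 0.7 and equals the stated 80% only near r = 0.5. The Summary and the Data analysis section describe the main comparison differently, and the calculation fits only one reading. A loss of power is possible but not demonstrated.

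The change-score figures assume the same SD at both visits, a target of 10.8 points and a range of correlations that the protocol does not supply. The matter should be corrected, but it does not call the number enrolled into question.

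**What to change.** 1. Name one primary comparison, in the same words, in the Summary and in Data analysis. The preferred choice is the six-month score compared between groups with adjustment for the baseline score, which the trial already collects and uses to stratify randomisation.
2. Restate the Sample size calculation: a difference of 10.8 points (30% of 36) in the six-month score; SD 21.6 at one time point, assumed to hold at six months; two-sided significance level 0.05; 64 evaluable per group for at least 80% power under the baseline-adjusted analysis. Say that 100 per group then allows a 36% loss.
3. If the t-test on change is kept, state the assumed correlation and its source, the resulting SD of change and the resulting power. Note that the tolerable loss from 100 per group depends on that correlation (36% at r = 0.5, 11% at r = 0.3).

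The cost is rewording in three sections and, for the preferred option, replacing the t-test with a simple regression model. No further data are needed. Enrolment is unchanged under the preferred option; if change is kept, whether 100 per group suffices depends on the correlation assumed and the loss expected.

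### The unadjusted before/after t-test uses only subjects who attend at six months, and extra recruitment protects its power but not its freedom from bias

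*Protocol*

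**What the plan says.** - **Protocol, Sample size calculation.** The baseline mean "score is 36, with a mean between-subject standard deviation of 21.6". From this, "a sample of 64 subjects per group is required". The protocol then enters 100 per group, and the reason given is "To ensure adequate numbers in each group at six months to permit appropriate analysis, and minimising the risk of type II error". No expected dropout rate is stated.
- **Protocol, Summary and Data analysis.** The Summary describes the outcome as the average change in the score, "as measured by Cariogram before and after the intervention between the test and control groups will be compared using a two-sample two-sided t-test". Data analysis names the same test for the score and the seven risk factors. Neither section mentions adjustment for baseline.
- **Protocol, Follow-up examination.** The six-month score comes from a second appointment that repeats the baseline procedures. Location of study places these visits in the subjects' own general dental practices.
- **Protocol, Specific objectives.** Objective 2 is "To assess whether there is an increase in patient engagement with the dentist". The Summary also presents the promotion of regular check-ups as part of what a successful personalised system would achieve.
- **Protocol, Intervention and Follow-up examination.** After baseline, Test subjects are posted their own Cariogram report and chart, while Controls are posted general information only. Controls receive their charts after the six-month assessment.

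**The concern.** A before/after comparison needs both scores, so a randomised subject who misses the second appointment drops out of the test as written. The protocol answers such loss only by entering more subjects. That restores power, but it does not restore the balance that randomisation gave.

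Attendance at the outcome visit is a post-randomisation behaviour, and the arms have different reasons to attend. Test subjects know their baseline risk when they decide whether to return; Controls have not yet been sent theirs. The personalised system is also meant to encourage dental attendance. If the two arms retain different kinds of patient, the difference among attenders no longer estimates the effect of allocation. The test could then show an effect where there is none, or hide a real one.

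**Working it through.** **1. The plan's own figure.** The target is 30% of 36, so 0.30 × 36 = 10.8 points. The standardised difference is 10.8 / 21.6 = 0.50. With two-sided alpha 0.05 (reading the protocol's margin of error as alpha) and 80% power, the normal approximation gives 63 per arm. The t-based calculation gives 63.77, rounded up to 64. The stated 64 reproduces. Power is 80.1% with 64 per arm analysed and 94.0% with 100.

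**2. Headroom.** 100 − 64 = 36 per arm, and 64 / (1 − 0.36) = 100. This is the largest loss that still leaves 80% power. It is not a loss the protocol says it expects.

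**3. Bias when attendance relates to baseline score.** None of the following assumptions is in the protocol:
- equal SDs of 21.6 at both visits and correlation r = 0.5 between them;
- no true effect;
- the same retention p in both arms;
- attendance driven by a normal variable whose correlation with baseline score is ρT in Test and ρC in Control.

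The SD of change is then 21.6 × √(2 × (1 − 0.5)) = 21.6, and the slope of change on baseline is r − 1 = −0.5. Attenders' mean baseline shifts by ρ × 21.6 × λ, where λ = φ(z)/p and z is the attendance cut-off. λ is 0.585 at p = 64% and 0.274 at p = 85%. So:

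bias (Test − Control) = 0.5 × 21.6 × λ × (ρC − ρT)

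| ρT, ρC | 64% retained | 85% retained |
|---|---|---|
| 0, 0.4 | 10.8 × 0.585 × 0.4 = 2.5 | 10.8 × 0.274 × 0.4 = 1.2 |
| −0.3, 0.3 | 10.8 × 0.585 × 0.6 = 3.8 | 10.8 × 0.274 × 0.6 = 1.8 |
| equal | 0 | 0 |

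**4. Bias when attendance relates to the subject's own change, in one arm only.** The bias is ρ × 21.6 × λ. For ρ = 0.3 this is 3.8 points at 64% and 1.8 at 85%.

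**5. Effect on the test.** With 64 per arm, SE = 21.6 × √(2/64) = 3.82. A bias of 2.5 points is 0.65 SE, and the two-sided type I error is about 10%. A bias of 3.8 points is 0.99 SE, giving about 17%. With 85 per arm, SE = 21.6 × √(2/85) = 3.31, and a bias of 1.2 points gives about 6.5%. Simulation with 100 entered per arm agrees: about 10% and 16 to 17% at 64% retention. For correlations 0 and 0.4 at 85% retention it gives a bias of 1.2 to 1.3 points and a type I error of 6.5%.

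**6. What use of the baseline score does.**
- Selection on baseline (step 3): adjusting the six-month score for baseline brings the bias to about 0 and the type I error to about 5%.
- Selection on own change (step 4, 64% retained): the bias falls only from about 3.8 to 2.8 points with baseline adjustment. Multiple imputation by arm from the baseline score also leaves about 2.8 points, with a type I error of 12%.

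**7. Precision.** At r = 0.5 the adjusted residual SD is 21.6 × √(1 − 0.25) = 18.7, so the standardised difference is 10.8 / 18.7 = 0.58. Power at 64 per arm rises from 80% to about 90%. With imputation by arm it is about 83%.

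**The case against.** **The SAP may cover this.** Analysis sets and missing-data rules are usually left to the SAP, which is not at hand, and a t-test can be run on imputed data. This stands as far as it goes: the lack of an imputation section is not the point. What remains is what the protocol does state, namely an unadjusted test that needs both scores and a treatment of six-month loss as a power matter only.

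**The 36% is not a planned loss.** A reader might infer that the trial expects to lose 36 of 100 per arm. The protocol does not say so. It gives two reasons for the larger number, and some of the surplus may simply be extra power. The bias must therefore be shown over a range of retention, and it shrinks as retention rises.

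**The design limits differential loss.** Both arms get weekly texts for 24 weeks, a €30 voucher on completion and their reports afterwards. The visit is a scheduled study appointment, and objective 2 does not define engagement as attending it. The better motivation to visit described under Potential risks and benefits is credited to taking part in the project, which covers both arms. These features make similar selection in both arms plausible, and bias is then nil. They do not remove the asymmetry in who knows their own risk before returning.

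**The remedy is partial.** This is correct. Methods that rely on baseline data do not cure selection on a subject's own change.

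**Conclusion.** The point holds as a weakness in the stated method, not as a demonstrated bias. The protocol fixes an unadjusted comparison that as written rests on attenders, offers only over-recruitment against six-month loss, and gives the arms different information before the outcome visit. On the assumptions shown, baseline-related selection could shift the result by about 1 to 4 points in either direction, against a 10.8-point target, and raise the type I error from 5% to between about 6.5% and 17%. Retention, the attendance correlations and r = 0.5 are all assumed. The bias is nil if selection is alike in both arms.

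A reader might go further and infer that the sample size is wrong, or that the result will be biased. The documents support neither: 64 reproduces, and loss alone, even at 36%, does not bias the comparison.

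**What to change.** 1. **Data analysis (and the matching Summary sentence).** For the main score, replace the unadjusted t-test with a comparison of subjects in their allocated arm that uses the baseline score already collected. Use either a model of the six-month score adjusted for baseline score, which is also the stratification variable, or multiple imputation by arm from the baseline score and the baseline risk-factor inputs.
2. **Report six-month attendance by arm.** This may also inform objective 2.
3. **Add a missing-not-at-random sensitivity analysis** that varies the assumed change in non-attenders separately by arm. Holding non-attenders at their baseline score and asking only for agreement in direction is too weak. With selection on own change at 64% retention, the no-change analysis had the same type I error as the attender t-test (16.8%), and the agreement rule stopped no false positive.
4. **State the limit.** Baseline adjustment or imputation removes bias from attendance related to baseline, but not bias from attendance related to the subject's own change.
5. **Sample size calculation.** Say that 100 per group guards against loss of precision only, and give the expected loss.

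The cost is wording and a little more analysis work. No new data, visits or subjects are needed.
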